13.4.2. ApoE Genotyping

Whole blood samples for deoxyribonucleic acid (DNA) ApoE genotyping will be collected from all subjects at the Screening Visit.

[REDACTED]

13.4.4. Health Outcomes Assessments

The following assessments will be performed to evaluate the effect of aducanumab in subjects and caregivers:

- EQ-5D (SR)
- EQ-5D (IR-S)
- [REDACTED]
- mPDQ-20
- [REDACTED]

Some tests will require the informant/care partner to participate and answer questions regarding the subject's daily activities and cognitive capabilities.

The recommended order of administration of the clinical assessments is described in the Study Reference Guide.

CONFIDENTIAL

The information contained herein may not be used, disclosed, or published without the written consent of Biogen MA Inc.

[REDACTED]

CONFIDENTIAL

The information contained herein may not be used, disclosed, or published without the written consent of Biogen MA Inc.

14. SAFETY ASSESSMENTS

See Section 4.2 for the timing of assessments.

14.1. Clinical Safety Assessments

The following clinical assessments will be performed to evaluate the safety profile of aducanumab:

- AE and SAE monitoring.
- Physical examination, including height and weight.
- Neurological examination.
- Vital signs (body temperature, heart rate, SBP, DBP, and respiratory rate).
- 12-lead ECG.
- Brain MRI.
- Concomitant medication, therapy, and procedure monitoring.
- MOCA (for ARIA monitoring and management).
- Columbia Suicide Severity Rating Scale (C-SSRS).

14.2. Laboratory Safety Assessments

The following laboratory assessments will be performed to evaluate the safety profile of aducanumab

- Hematology: complete blood count with differential and platelet count, and absolute neutrophil count.
- Blood chemistry: total protein, albumin, creatinine, blood urea nitrogen, uric acid, bilirubin (total and direct), alkaline phosphatase, ALT, AST, lactate dehydrogenase, gamma-glutamyl-transferase, glucose, calcium, phosphorus, bicarbonate, chloride, sodium, and potassium.
- Urinalysis: color, specific gravity, pH, protein, glucose, blood, ketones, and microscopic examination (if abnormal).
- Serum and urine pregnancy test for women of childbearing potential only.
- Coagulation, virology (including HIV at the Investigator's discretion after consideration of risk factors), HbA_{1c}, and alcohol/drug screen at Screening.

CONFIDENTIAL

The information contained herein may not be used, disclosed, or published without the written consent of Biogen MA Inc.

14.3. Immunogenicity Assessments

Presence of serum anti-aducanumab will be determined using a validated assay. A standard 3-tier antidrug antibody (ADA) approach will be used (i.e., screening assay, confirmatory assay, and titration assay). Additional characterization of the immune response may be performed.

CONFIDENTIAL

The information contained herein may not be used, disclosed, or published without the written consent of Biogen MA Inc.

15. SAFETY DEFINITIONS, RECORDING, REPORTING, AND RESPONSIBILITIES

Throughout the course of the study, every effort must be made to remain alert to possible AEs. If an AE occurs, the first concern should be for the safety of the subject. If necessary, appropriate medical intervention should be provided.

At the signing of the ICF, each subject or his/her legally authorized representative must be given the names and telephone numbers of study site staff for reporting AEs and medical emergencies.

15.1. Definitions

15.1.1. Adverse Event

An AE is any untoward medical occurrence in a patient or clinical investigation subject administered a pharmaceutical product and that does not necessarily have a causal relationship with this treatment. An AE can therefore be any unfavorable and unintended sign (including an abnormal laboratory finding), symptom, or disease temporally associated with the use of a medicinal (investigational) product, whether or not related to the medicinal (investigational) product.

Determination of whether an abnormal laboratory value meets the definition of an AE will be made by the Investigator. Although abnormal laboratory values are typically not considered AEs, the following considerations may result in an abnormal laboratory value being considered an AE:

- A laboratory test result that meets the criteria for an SAE.
- A laboratory test result that requires the subject to receive specific corrective therapy.
- A laboratory abnormality that the Investigator considers to be clinically significant.

Pre-treatment, nonserious AEs that occur within 48 hours after receipt of a ligand will be captured by the sites on the AE form.

15.1.2. Serious Adverse Event

An SAE is any untoward medical occurrence that at any dose:

- Results in death.
- In the view of the Investigator, places the subject at immediate risk of death (a life-threatening event); however, this does not include an event that, had it occurred in a more severe form, might have caused death.
- Requires inpatient hospitalization or prolongation of existing hospitalization.
- Results in persistent or significant disability/incapacity.
- Results in a congenital anomaly/birth defect.

CONFIDENTIAL

The information contained herein may not be used, disclosed, or published without the written consent of
Biogen MA Inc.

An SAE may also be any other medically important event that, in the opinion of the Investigator, may jeopardize the subject or may require intervention to prevent one of the other outcomes listed in the definition above. (Examples of such medical events include allergic bronchospasm requiring intensive treatment in an emergency room or convulsions occurring at home that do not require an inpatient hospitalization.)

15.1.3. Prescheduled or Elective Procedures or Routinely Scheduled Treatments

A prescheduled or elective procedure or a routinely scheduled treatment will not be considered an SAE, even if the subject is hospitalized. The study site must document all of the following:

- The prescheduled or elective procedure or routinely scheduled treatment was scheduled (or was on a waiting list to be scheduled) prior to obtaining the subject's consent to participate in the study.
- The condition requiring the prescheduled or elective procedure or routinely scheduled treatment was present before and did not worsen or progress in the opinion of the Investigator between the subject's consent to participate in the study and the time of the procedure or treatment.
- The prescheduled or elective procedure or routinely scheduled treatment is the sole reason for the intervention or hospital admission.
 - If a subject is hospitalized due to local requirements for administration of the study treatment, the hospitalization should not be considered an SAE unless one of the requirements in Section 15.1.2 is met.

15.2. Safety Classifications

15.2.1. Investigator Assessment of Events

All events must be assessed to determine the following:

- If the event meets the criteria for an SAE as defined in Section 15.1.2.
- The relationship of the event to study treatment as defined in Section 15.2.2.
- The severity of the event as defined in Section 15.2.3.

CONFIDENTIAL

The information contained herein may not be used, disclosed, or published without the written consent of Biogen MA Inc.

15.2.2. Relationship of Events to Study Treatment

The following definitions should be considered when evaluating the relationship of AEs and SAEs to the study treatment.

Relationship of Event to Study Treatment	
Not related	An AE will be considered "not related" to the use of the investigational drug if there is not a reasonable possibility that the event has been caused by the product under investigation. Factors pointing toward this assessment include but are not limited to: the lack of reasonable temporal relationship between administration of the drug and the event, the presence of a biologically implausible relationship between the product and the AE, or the presence of a more likely alternative explanation for the AE.
Related	An AE will be considered "related" to the use of the investigational drug if there is a reasonable possibility that the event may have been caused by the product under investigation. Factors that point toward this assessment include but are not limited to: a positive rechallenge, a reasonable temporal sequence between administration of the drug and the event, a known response pattern of the suspected drug, improvement following discontinuation or dose reduction, a biologically plausible relationship between the drug and the AE, or a lack of an alternative explanation for the AE.

15.2.3. Severity of Events

The following definitions should be considered when evaluating the severity of AEs and SAEs:

Severity of Event	
Mild	Symptom(s) barely noticeable to subject or does not make subject uncomfortable; does not influence performance or functioning; prescription drug not ordinarily needed for relief of symptom(s) but may be given because of personality of subject.
Moderate	Symptom(s) of a sufficient severity to make subject uncomfortable; performance of daily activity is influenced; subject is able to continue in study; treatment for symptom(s) may be needed.
Severe	Symptom(s) cause severe discomfort; symptoms cause incapacitation or significant impact on subject's daily life; severity may cause cessation of treatment with study treatment; treatment for symptom(s) may be given and/or subject hospitalized.

15.2.4. Expectedness of Events

Expectedness of all AEs will be determined by Biogen according to the IB for aducanumab.

15.3. Monitoring and Recording Events

15.3.1. Adverse Events

Any AE experienced by the subject between the time of first dose of study treatment and the subject's final clinic visit (including FU Visit) is to be recorded on the CRF, regardless of the severity of the event or its relationship to study treatment. Pre-treatment, nonserious AEs that occur within 48 hours after receipt of a ligand will be captured by the sites on the AE form.

CONFIDENTIAL

The information contained herein may not be used, disclosed, or published without the written consent of Biogen MA Inc.

15.3.2. Adverse Events of Special Interest

ARIA-E and ARIA-H are considered AEs of special interest and will be entered on the Adverse Event of Special Interest CRF within 72 hours following the receipt of abnormal MRI findings from the central MRI reader.

AE reporting for ARIA-E and ARIA-H will be based on the following centrally read MRI sequences: fluid attenuated inversion recovery/T2 for ARIA-E and T2*/gradient echo for ARIA-H.

If the event qualifies as an SAE an SAE form should be submitted per the guidelines in Section 15.3.4. Investigators should include a copy of the centrally read MRI report when submitting the SAE form to [REDACTED].

15.3.3. Serious Adverse Events

Any SAE experienced by the subject between signing of the ICF and the subject's final clinic visit (including FU Visit) will be recorded on an SAE form, regardless of the severity of the event or its relationship to study treatment. SAEs must be reported to Biogen (or designee) within 24 hours as described in Section 15.3.4. This also applies to SAEs that occur after administration of the ligand. FU information regarding an SAE also must be reported within 24 hours.

Events occurring after the subject's final clinic visit (including FU Visit) should be reported to Biogen only if the Investigator considers the SAE related to study treatment.

Any SAE that is ongoing when the subject completes or discontinues the study will be followed by the Investigator until the event has resolved, stabilized, or returned to baseline status.

15.3.4. Immediate Reporting of Serious Adverse Events

In order to adhere to all applicable laws and regulations for reporting an SAE, the study site must formally notify [REDACTED] within 24 hours of the study site staff becoming aware of the SAE. It is the Investigator's responsibility to ensure that the SAE reporting information and procedures are used and followed appropriately.

Reporting Information for SAEs

Any SAE that occurs between the time that the subject has signed the ICF and the subject's final clinic visit (including FU Visit) must be reported to [REDACTED] within 24 hours of the study site staff becoming aware of the event. Thereafter, the event should be reported only if the Investigator considers it related to study treatment.

A report ***must be submitted*** to [REDACTED] regardless of the following:

- Whether or not the subject has undergone study-related procedures
- Whether or not the subject has received study treatment
- The severity of the event

CONFIDENTIAL

The information contained herein may not be used, disclosed, or published without the written consent of Biogen MA Inc.

- The relationship of the event to study treatment

To report initial or FU information on an SAE, fax or email a completed SAE form. Refer to the Study Reference Guide for country-specific [REDACTED] fax numbers or email [REDACTED].

15.3.4.1. Deaths

Death is an outcome of an event. The event that resulted in death should be recorded on the appropriate CRF. All causes of death must be reported as SAEs within 24 hours of the site becoming aware of the event. The Investigator should make every effort to obtain and send death certificates and autopsy reports to [REDACTED]. The term death should be reported as an SAE only if the cause of death is not known and cannot be determined.

15.3.5. Suspected Unexpected Serious Adverse Reactions

Suspected unexpected serious adverse reactions (SUSARs) are SAEs that are unexpected and judged by the Investigator or Biogen to be related to the study treatment administered.

Appropriate personnel in Biogen Safety and Benefit Risk (SABR) will unblind SUSARs for the purpose of regulatory reporting. Biogen or designee will submit SUSARs (in blinded or unblinded fashion) to regulatory agencies according to local law. Biogen or designee will submit SUSARs to Investigators in a blinded fashion.

15.4. Procedures for Handling Special Situations

15.4.1. Pregnancy

Subjects should not become pregnant or impregnate their partners during the study and for 24 weeks after their last dose of study treatment. If a female subject becomes pregnant, study treatment must be discontinued *immediately*.

The Investigator must report a pregnancy occurring in a female subject by faxing the appropriate form to [REDACTED] within 24 hours of the study site staff becoming aware of the pregnancy at the SAE reporting fax number provided in the study reference manual. The Investigator or study site staff must report the outcome of the pregnancy to [REDACTED].

Congenital abnormalities and birth defects in the offspring of male or female subjects should be reported as an SAE if conception occurred during the study treatment period.

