7.3. Overall Study Duration and Follow-Up

The study period will consist of Screening, treatment, and FU.

The double-blind, placebo-controlled period of the study will consist of an 8-week screening period, a 76-week treatment period, and a safety FU period of 18 weeks after the final dose.

Subjects will have approximately 32 scheduled clinic visits during the placebo-controlled period, and up to 8 telephone safety FU contacts, as follows:

- Screening Visits no more than 60 days before the first dose of study treatment on Day 1 (visits will be conducted on multiple days). It is recommended that all screening procedures be completed within 60 days; however, the overall screening period may be extended up to 90 days in the event of logistical issues related to PET scans and is subject to Sponsor approval.
- 20 outpatient dosing visits.
- 8 telephone safety FU contacts approximately 2 weeks after each of the first 8 doses.
- 3 visits for clinical assessments.
- [REDACTED]
- 3 visits (including Screening) for amyloid PET scan (in a subset of subjects).
- [REDACTED]
- 7 visits for brain MRI.

CONFIDENTIAL

The information contained herein may not be used, disclosed, or published without the written consent of Biogen MA Inc.

- 1 FU safety visit at Week 94 (only for subjects not entering the LTE period) or 18 weeks after last administration of study treatment for those subjects who withdraw from study.

Subjects who meet the LTE inclusion and exclusion criteria will be eligible to enter the LTE period. Subjects who enter the LTE period will have approximately up to 76 additional planned clinic visits, and up to 8 telephone safety FU contacts, as follows:

- 65 outpatient dosing visits.
- 8 telephone safety FU contacts approximately 2 weeks after each of the first 8 doses.
- 7 visits for clinical assessments.
- [REDACTED]
- 4 visits for amyloid PET scan (in a subset of subjects).
- [REDACTED]
- 10 visits for brain MRI.
- 1 FU safety visit.

Subjects who have a change in AD medication (other than study treatment) during the placebo-controlled or LTE period should have an unscheduled visit; all clinical assessments for the primary and secondary endpoints should be performed prior to the change in medication.

Subjects who experience ARIA during the placebo-controlled or LTE period should have unscheduled visits per the guidelines in Section 7.2.1.

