7.3.3. Follow-Up

All subjects participating in the placebo-controlled period are to return to the study site approximately 2 weeks after the final dose for clinical assessments.

Subjects participating in the placebo-controlled period and not entering the LTE period are to return to the study site for a FU Visit at Week 94 (18 weeks after the last placebo-controlled period dose). The final study visit for these subjects will be Week 94.

Subjects who participate in the LTE period are to return to the study site to receive their first LTE dose approximately 4 weeks after their last dose in the placebo-controlled period of the study. A FU Visit will occur 18 weeks after the last LTE period dose. The timing of the final study visit for subjects participating in the LTE period will vary, since the EOT Visit for a subject who participates in the LTE period will occur at Week 338, or when the last subject has had his or her Week 182 Visit, whichever occurs first.

Subjects who discontinue treatment are to remain in the study, attend a FU Visit 18 weeks after the final dose, and immediately continue protocol-required tests and assessments at a subset of

CONFIDENTIAL

The information contained herein may not be used, disclosed, or published without the written consent of
Biogen MA Inc.

the clinic visits (see Table 10 and Table 11) until the end of the study or until withdrawal of consent. Subjects who withdraw from the study are encouraged to return for FU assessments 18 weeks after their last dose of study treatment.

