8. SELECTION OF SUBJECTS

8.1. Inclusion Criteria

To be eligible to participate in this study, candidates must meet the following eligibility criteria at Screening or at the timepoint specified in the individual eligibility criterion listed:

1. Ability to understand the purpose and risks of the study and provide signed and dated informed consent and authorization to use confidential health information in accordance with national and local subject privacy regulations.
2. Aged 50 to 85 years old, inclusive, at the time of informed consent.
3. All women of childbearing potential and all men must practice highly effective contraception during the study and for 24 weeks after their last dose of study treatment. For further details of contraceptive requirements for this study, please refer to Section 15.5.
4. Must have at least 6 years of education or work experience to exclude mental deficits other than MCI or mild AD.
5. Must have a positive amyloid PET scan. Previously obtained PET scan (within 12 months of Screening) is permissible for subjects not participating in the amyloid PET substudy. Previous PET scan images must be submitted to the central imaging vendor to confirm study inclusion criteria are met.
6. Must meet all of the following clinical criteria for MCI due to AD or mild AD according to NIA-AA criteria [Albert 2011; McKhann 2011], and must have:
 - A CDR global score of 0.5.
 - An RBANS score of 85 or lower indicative of objective cognitive impairment (based upon the Delayed Memory Index score).
 - An MMSE score between 24 and 30 (inclusive).
7. Apart from a clinical diagnosis of early AD, the subject must be in good health as determined by the Investigator, based on medical history and screening assessments.
8. Must consent to ApoE genotyping.
9. Has one informant/care partner who, in the Investigator's opinion, has frequent and sufficient contact with the subject as to be able to provide accurate information about the subject's cognitive and functional abilities. The informant/care partner must minimally be available by phone to provide information to the Investigator and study staff about the subject and agrees to attend in person clinic visits that require partner input for scale completion. An informant/care partner should be available for the duration of the study, and the use of the same informant/care partner for the duration of the study is encouraged.

CONFIDENTIAL

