8.3. Inclusion Criteria for Long-Term Extension Period

To be eligible to participate in the LTE period, subjects must meet the following eligibility criteria at Week 78:

1. Subject must have completed the placebo-controlled period of the study including the Week 78 Visit. Subject must have taken at least 14 doses and not have missed more than 4 consecutive doses, except for subjects whose dose was suspended due to ARIA (See Section 7.2.1). Subjects who do not meet these criteria may enter the LTE period only with Sponsor's approval.
2. The subject (or the subject's legally authorized representative) has the ability to understand the purpose and risks of the study and provide signed and dated informed consent (or assent) and authorization to use confidential health information in accordance with national and local subject privacy regulations.
3. Female subjects of childbearing potential and male subjects must practice highly effective contraception during the study and for 24 weeks after their last dose of study treatment.
4. Apart from a clinical diagnosis of AD, the subject must be in good health as determined by the Investigator, based on medical history.
5. Must have the ability to comply with procedures for protocol-related tests.

CONFIDENTIAL

The information contained herein may not be used, disclosed, or published without the written consent of Biogen MA Inc.

6. Has one informant/care partner who, in the Investigator's opinion, has frequent and sufficient contact with the subject as to be able to provide accurate information about the subject's cognitive and functional abilities. The informant/care partner must minimally be available by phone to provide information to the Investigator and study staff about the subject and agrees to attend in person clinic visits that require partner input for scale completion. An informant/care partner should be available for the duration of the study, and the use of the same informant/care partner for the duration of the study is encouraged.

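### Section 15.4.1 ties birth-defect SAE reporting to conception during treatment, although the same section bars conception until 24 weeks after the last dose

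*Protocol*

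**What the plan says.** The protocol (Version 6.0) sets one avoidance period for both sexes. Section 15.4.1 opens: "Subjects should not become pregnant or impregnate their partners during the study and for 24 weeks after their last dose of study treatment". The entry criteria agree. Section 8.1 requires women of childbearing potential and all men to "practice highly effective contraception during the study and for 24 weeks after their last dose of study treatment", and Section 8.3 repeats this for the long-term extension (LTE): "contraception during the study and for 24 weeks after their last dose of study treatment".

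The last sentence of Section 15.4.1 covers congenital abnormalities and birth defects in the offspring of male or female subjects. These "should be reported as an SAE if conception occurred during the study treatment period".

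The study treatment period has no separate definition, but Section 7.3 describes the placebo-controlled part, after screening, as "a 76-week treatment period, and a safety FU period of 18 weeks after the final dose". Treatment and follow-up are distinct phases. For subjects who do not enter the LTE, Section 7.3.3 adds: "The final study visit for these subjects will be Week 94". For those who do: "A FU Visit will occur 18 weeks after the last LTE period dose".

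Pregnancy reporting in Section 15.4.1, and the outcome follow-up in Section 15.6.1, are written for female subjects. Neither has an end date. After the final visit, Section 15.3.3 says that SAEs "should be reported to Biogen only if the Investigator considers the SAE related to study treatment".

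**The concern.** The first and last sentences of Section 15.4.1 use different windows for related purposes. One asks subjects to avoid conception until 24 weeks after the last dose. The other makes a birth defect an SAE when conception fell within treatment. A site that reads the last sentence literally could decide that a defect conceived a few weeks after the last infusion need not go in as an SAE, although the subject was still being told not to conceive.

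What is at stake is safety capture. Such outcomes will be rare, so each one carries weight, and the rule for recording them should be unambiguous. The exposed group is mainly the offspring of male subjects. Men are bound by the 24-week period and defects in their children are meant to be reported, yet no step tells the site to report a partner's pregnancy.

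**Working it through.** **Inputs.** Last dose and follow-up visit: Days 533 and 659 (Tables 2 and 3), and Days 2353 and 2479 (Table 9). Avoidance period: 24 weeks after the last dose (Sections 8.1, 8.3, 15.4.1). Half-life: 16 to 24 days (Section 7.1).

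**1. Reproduce the stated follow-up interval.**
- Placebo-controlled period: 659 − 533 = 126 days; 126 / 7 = 18.0 weeks.
- LTE: 2479 − 2353 = 126 days = 18.0 weeks.

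Both match the protocol's 18 weeks.

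**2. Length of the avoidance period after the last dose.** 24 × 7 = 168 days. It ends at Week 76 + 24 = 100, or at Week 336 + 24 = 360 for a full LTE. That is 168 − 126 = 42 days, or 6 weeks, after the last visit.

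**3. Size of the mismatch.** If the treatment period ends at the last infusion, as Section 7.3 implies, the reporting sentence reaches 0 weeks beyond it. The mismatch is 24 − 0 = 24 weeks: 18 before the final visit and 6 after. If a generous reader lets treatment run on for one four-week dosing interval, it is 24 − 4 = 20 weeks.

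**4. Drug remaining (context only).** Assuming simple first-order elimination, the fraction left 28 days after an infusion is 0.5^(28/t½): 0.30 at 16 days, 0.38 at 20 days and 0.45 at 24 days. This describes exposure. It does not count lost reports.

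**5. Do other rules close the gap?**
- *Female subjects.* A woman who conceives 4 weeks after the last infusion is 18 − 4 = 14 weeks past conception at the follow-up visit, where a urine pregnancy test is scheduled for women of childbearing potential (Tables 2 and 9). The pregnancy is then reportable within 24 hours of the site learning of it, and its outcome must follow. What stays open is whether a defect also has to be filed as an SAE.
- *Offspring of male subjects.* No pregnancy or outcome report is required. Section 15.1.2 lists congenital anomaly among the SAE criteria, but Section 15.3.3 collects SAEs that the subject experiences, which does not clearly reach a man's child.
- *After the final visit.* For a subject who completes dosing, any birth more than 18 weeks after a post-treatment conception falls after the last visit. From then on, SAE reporting depends on the investigator's view of relatedness.
- *Early stoppers.* Subjects who stop dosing but stay in the study are seen later. With a last dose at Week 24, the Week 78 visit is 78 − 24 = 54 weeks after it.

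**The case against.** The strongest reply is that little is actually lost.

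- The sentence says *if*, not *only if*, so it forbids no report.
- For women, pregnancy and outcome reporting is open-ended, so the information reaches the sponsor whether or not it carries an SAE label.
- Related SAEs remain reportable after the final visit without a time limit, and Section 15.2.2 asks only for a reasonable possibility of causation.
- A contraception margin longer than safety follow-up is not itself an error. Section 7.1 gives the 18 weeks its own rationale.

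All of this stands, and it rules out stronger readings. A reader might infer that post-treatment conceptions are excluded from the safety database by rule; for female subjects the outcome-reporting duty shows otherwise. A reader might infer that sites have no way to learn of a partner's pregnancy; men attend visits every four weeks and again at 18 weeks, so what is missing is a written reporting step, not contact. A reader might also take the difference between 18 and 24 weeks as a contradiction. It is not one, and the 18-week last visit applies only to those who complete dosing.

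The reply does not explain why two sentences of one short section use different windows, or what a site should do about a male subject's partner.

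**Conclusion.** The point holds as an internal inconsistency in Section 15.4.1. The conception window for birth-defect SAE reporting is up to 24 weeks shorter than the protocol's own avoidance period for a subject who completes dosing (20 weeks on the generous reading of treatment). Defects conceived in that interval are not required by that sentence to be reported as SAEs. The gap is partly closed for female subjects and widest for the offspring of male subjects.

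This rests on reading the treatment period as separate from follow-up, as Section 7.3 presents it. The protocol describes a contraception and avoidance period; it does not state how large any risk is, and nothing here judges whether 24 weeks is the right length. The point is minor: events will be few at ages 50 to 85, and no endpoint, error rate or power figure changes.

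**What to change.** Reconcile the two sentences of Section 15.4.1 so that the conception window for reporting birth defects as SAEs matches the protocol's own avoidance period: during the study and for 24 weeks after the last dose. In the same section, state whether pregnancies in partners of male subjects are to be reported over that window.

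The core change is one sentence, plus a second on partner pregnancies. It adds no visit or procedure, but it has to go through the amendment process in Section 19.3 and could be carried with the next amendment. If the sponsor decides to collect partner pregnancies, the partner's consent has to be arranged. A telephone contact at 24 weeks for the few subjects concerned would be an optional extra, and the correction does not depend on it.
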